7.2. Lost to Follow-up

A subject will be considered lost to follow-up if he or she repeatedly fails to return for scheduled visits and is unable to be contacted by the study site. The following actions must be taken if a subject fails to return to the clinic for a required study visit:

- The site must attempt to contact the subject and reschedule the missed visit as soon as possible and counsel the subject on the importance of maintaining the assigned visit schedule and ascertain whether or not the subject wishes to and/or should continue in the study.
- Before a subject is deemed lost to follow up, the investigator or designee must make every effort to regain contact with the subject (where possible, 3 telephone calls and, if necessary, a certified letter to the subject's last known mailing address or local

equivalent methods). These contact attempts should be documented in the subject's medical record.

- Should the subject continue to be unreachable, he/she will be considered to have withdrawn from the study.

Discontinuation of specific sites or discontinuation of the study is handled as indicated in [Section 10.8](#).

8. STUDY ASSESSMENTS AND PROCEDURES

8.1. Visit Details

The Schedule of Events and Procedures [Table 3](#) provides a high-level overview of the visits. The sections below provide visit guidance/details by visit.

8.1.1. Visit 1 (Screening)

- Explain the purpose and conduct of the study to the subject and obtain written individual informed consent. Informed consent for the optional PGx consent may sign at screening yet laboratory research study must be obtained after subject Visit 2 (Baseline, Day 1) at any visit. Ensure the subject understands that if he/she does not wish to provide a blood sample for the PGx laboratory research study that their decision will have no influence on their participation in the main study.
- Prepare the list of screening/registration of subjects.
- Obtain demographics.
- Obtain medications, procedures/therapies, and medical history including all lifetime ocular medical history to the extent possible, non-ocular medical history within 5 years, diagnosis, ocular surgical history, current ocular, and systemic conditions.
- Obtain urine and perform a urine pregnancy test, if the subject is a female of child-bearing potential.
- Query the subject regarding AEs
- As per Schedule of Events and Procedures ([Table 3](#)), perform the following procedures or assessments (all ophthalmic procedures to be performed in both eyes):
 - Vital signs (blood pressure/pulse rate)
 - Refraction
 - BCVA (before IOP measurement)
 - Slit-lamp biomicroscopy (before IOP measurement)
 - IOP
 - Pachymetry (after IOP measurement)
 - Gonioscopy (only if no gonioscopy was performed within 3 months [90 days] prior to screening and documented in the subject's records). If needed, gonioscopy will be performed after IOP measurement.
 -
 - Visual field (only if no visual field test was performed within 3 months [90 days] prior to screening and documented in the subject's records). If needed, visual field test will be performed before IOP, pachymetry, and gonioscopy (if applicable).
 - Ophthalmoscopy with pupil dilation (after IOP measurement)

- Determine if the subject meets eligibility criteria.
- If the subject meets eligibility criteria and is still willing to continue the study, discontinue current IOP-lowering medications, if any, according to the following schedule (up to +7 days as a window is allowed):
 - Miotics: 7 days
 - Oral/topical CAIs: 7 days
 - Alpha agonists: 14 days
 - Alpha/beta agonists: 14 days
 - Alpha antagonists (α 1 blocker): 28 days
 - Beta antagonists (β blocker, including $\alpha\beta$ blockers): 28 days
 - Prostaglandin Analogs: 28 days
 - Rho kinase inhibitor: 28 days
 - Combination drugs: The longest washout period of the individual component will be used. Please note: Subjects are only allowed to be treated with a maximum of two active ingredients for IOP reduction prior to screening.
- During the required washout period, subjects who discontinue their current treatment may, if the Investigator deems it necessary for safety, be treated with a topical CAI, e.g., brinzolamide or dorzolamide eye drops, one drop twice daily. Topical CAI treatment must stop 7 days before the randomization at Visit 2 (Baseline, Day 1).
- An interim safety visit, mid-washout visit (Optional Visit 1a), may be performed during the washout period if, in the Investigator's opinion, a subject's IOP causes any safety concerns during the washout period. If subjects are to be treated with topical CAI in the week before Visit 2 (Baseline, Day 1), mid washout visit (Optional Visit 1a) is recommended to be performed.
- The eligibility visit (Visit 2 (Baseline, Day 1)) will be scheduled at the end of the washout period for those subjects on prior IOP-lowering medications.
- Subjects who have not used an IOP-lowering medication for the last 28 days, including treatment-naïve subjects, may be combined Visit 1 (Screening) and Visit 2 (Eligibility/Baseline, Day 1) into one visit. Subjects must fulfill on the day of this combined visit; in particular, full diurnal IOP measurements (at 08:00, 10:00, 16:00) must be taken.
 - If a subject does not require washout from an IOP-lowering medication, but they use contact lenses in either eye, they will need a wait period of \geq 1-2 weeks (1 week for soft contact lens wearers, and 2 weeks for rigid contact lens wearers) with no contact use before their Visit 2 (Baseline, Day 1).
- Schedule the eligible subject to return for Visit 2 (Baseline, Day 1) after the required wait/washout period.

- A subject who does not meet eligibility criteria or will not otherwise continue in the study is considered a screen failure.

8.1.2. Optional Visit 1a

- Optional Visit 1a is an interim safety visit (referred to as mid-washout visit) that may be performed during the washout period if, in the Investigator's opinion, a subject's IOP causes any safety concern during washout period.
- Update concomitant medications and procedures/therapies.
- Query the subject regarding AEs.
- As per Schedule of Events and Procedures ([Table 3](#)), perform the following procedures or assessments (all ophthalmic procedures to be performed in both eyes):
 - BCVA (before IOP measurement)
 - Slit-lamp biomicroscopy (before IOP measurement)
 - IOP

8.1.3. Visit 2 (Baseline, Day 1)

- Update concomitant medications and procedures/therapies.
- Confirm the subject has complied with the required wait/washout period for ocular hypotensive medication(s), or contact lenses use, if required.
- Query the subject regarding AEs.
- As per Schedule of Events and Procedures ([Table 3](#)), perform the following procedures or assessments immediately before the 08:00 (± 60 min) IOP measurement (all ophthalmic procedures to be performed in both eyes):
 - BCVA (before the 08:00 (± 60 min) IOP measurement).
 - If more than 10 letters in BCVA were lost compared to the screening visit, then refraction should be performed again.
 - Slit-lamp biomicroscopy (before the 08:00 (± 60 min) IOP measurement).
 - Perform vital signs (blood pressure/pulse rate) measurements (before the 08:00 (± 60 min) IOP measurement).
 - Obtain urine and perform a urine pregnancy test, if the subject is a female of childbearing potential (before the 08:00 (± 60 min) IOP measurement).
- Perform IOP measurement at 08:00 (± 60 min).
- If subject meets the 08:00 IOP eligibility requirements, schedule additional IOP measurements at 10:00.
- Perform IOP measurement at 10:00 (± 60 min).
- If subject meets the 08:00 and 10:00 IOP eligibility requirements, schedule additional IOP measurements at 16:00.

- Perform GQL-15 questionnaire at any time during this visit prior to 16:00 IOP measurement.
- Perform IOP measurement at 16:00 (± 60 min).
- Perform pupil dilation in both eyes after the 16:00 (± 60 min) IOP measurement.
- Perform ophthalmoscopy with pupil dilation in both eyes immediately after the 16:00 (± 60 min) IOP measurement.
- Perform final review of eligibility criteria after the 16:00 (± 60 min) IOP measurement. The subject will then be randomized, via Medidata Rave RTSM.
- A subject who does not meet eligibility criteria or will not otherwise continue in the study is considered a screen failure.
- After the subject has been randomized to a treatment arm, and assigned a treatment kit by Medidata Rave RTSM, an authorized unmasked study staff member, other than the Investigator or Examiner, must:
 - Dispense the assigned kit to the subject which will contain the following:
 - Two bottles of study drug labeled “morning” and
 - Two bottles of study drug labeled “evening”
 - OR
 - Two bottles of study drug labeled morning/evening.
 - Give the subject verbal and written instructions for proper instillation of the study medication, the dosing regimen, and study medication storage.
 - Provide paper subject diary to subject and provide instructions to record daily medication instillation.
 - Instruct the subject not to show or discuss their study medication with other study staff including the Investigator or Examiner, or other study subjects.
- Instruct the subject to instill the study medicine daily in both eyes, starting from this evening (“evening” dose) (20:00).
- Schedule the subject to return on Visit 3 (Week 2, Day 14 ± 3).
- Inform the subjects they will be reminded of the evening instillation of the study medication by a phone call a few days before Visit 3 (Week 2).
- Remind the subjects that the morning dose of Visit 3 (Week 2) will be done at the site.

8.1.4. Visit 3 (Week 2, Day 14 ± 3)

- Update concomitant medications and procedures/therapies.
- An authorized unmasked study staff member, other than the Investigator or Examiner should query the subject regarding dosing compliance, check the subject paper diary

of daily medication recording, and ensure subject has sufficient study medication to complete dosing through Visit 4 (Week 6).

- Query the subject regarding AEs.
- As per Schedule of Events and Procedures ([Table 3](#)), perform the following procedures or assessments immediately before the 08:00 (± 60 min) IOP measurement (all ophthalmic procedures to be performed in both eyes):
 - BCVA (before the 08:00 (± 60 min) IOP measurement)
 - If more than 10 letters in BCVA were lost compared to the screening visit, then refraction should be performed again.
 - Slit-lamp biomicroscopy (before the 08:00 (± 60 min) IOP measurement)
- Perform IOP measurement at 08:00 (± 60 min).
- Instill study medication/eye drop after the 08:00 IOP measurement in both eyes. Authorized unmasked study staff should make sure the instillation is performed. Record the morning medication in the subject diary.
- Perform IOP measurement at 10:00 (± 60 min), and 16:00 (± 60 min).
- If the subject provided written consent to provide a blood sample for a future PGx laboratory research study, collect the sample at this visit or subsequent visit prior to exit from the study.
 - Note: If a blood sample cannot be collected at this visit, it may be collected at any one of the following visits, for example, Visit 4, 5, or unscheduled or early termination visit, provided the subject has written consent prior to collection of the sample.
- Schedule the subject to return on Day 42 \pm 3 for Visit 4 (Week 6).
- Remind the subject to continue dosing according to the written instructions.
- Inform the subjects they will be reminded of the evening instillation of the study medication by a phone call a few days before Visit 4 (Week 6).
- Remind the subjects that the morning dose of Visit 4 (Week 6) will be done at the site.
- Remind the subject to bring all used and unused study medication and subject diary at Visit 4 (Week 6).

8.1.5. Visit 4 (Week 6, Day 42 \pm 3)

- Update concomitant medications and procedures/therapies.
- An authorized unmasked study staff member, other than the Investigator or Examiner should query the subject regarding dosing compliance and check the subject paper diary of daily medication recording.
- Query the subject regarding AEs.

- As per Schedule of Events and Procedures ([Table 3](#)), perform the following procedures or assessments immediately before the 08:00 (± 60 min) IOP measurement (all ophthalmic procedures to be performed in both eyes):
 - BCVA (before the 08:00 (± 60 min) IOP measurement)
 - If more than 10 letters in BCVA were lost compared to the screening visit, then refraction should be performed again.
 - Slit-lamp biomicroscopy (before the 08:00 (± 60 min) IOP measurement)
 - Obtain urine and perform a urine pregnancy test if the subject is a female of childbearing potential (before the 08:00 (± 60 min) IOP measurement).
- Perform IOP measurement at 08:00 (± 60 min).
- Instill study medication/eye drop after the 08:00 IOP measurement in both eyes. Authorized unmasked study staff should make sure the instillation is performed. Record the morning medication in subject diary.
- Perform IOP measurement at 10:00 (± 60 min), and 16:00 (± 60 min).
- An authorized unmasked study staff member, other than the Investigator or Examiner, must:
 - Collect all used and unused bottles of study medication.
 - Collect the paper subject diary.
- Dispense the assigned kit (from Medidata Rave RTSM) to the subject which will contain the following:
 - Two bottles of study drug labeled “morning” and
 - Two bottles of study drug labeled “evening”
 - OR
 - Two bottles of study drug labeled morning/evening.
 - Instruct the subject not to show or discuss their study medication with other study staff including the Investigator or Examiner, or other study subjects.
 - Provide paper subject diary to subject and provide instructions to record daily medication instillation.
- If the subject provided written consent to provide a blood sample for a future PGx laboratory research study, the sample may be collected at this visit or subsequent visit prior to exit from the study, if not collected at the previous visit.
- Schedule the subject to return on Day 90 \pm 7 for Visit 5 (Month 3).
- Remind the subject to continue dosing according to the written instructions.
- Inform the subjects they will be reminded of the evening instillation of the study medication by a phone call a few days before Visit 5 (Month 3).

- Remind the subjects that the morning dose of Visit 5 (Month 3) will be done at the site.
- Remind the subject to bring all used and unused study medication and subject diary at Visit 5 (Month 3).

8.1.6. Visit 5 (Month 3, Day 90 ±7) / Study Exit/ Early Termination

- Update concomitant medications and procedures/therapies.
- An authorized unmasked study staff member, other than the Investigator or Examiner should query the subject regarding dosing compliance and check the subject paper diary of daily medication recording.
- Query the subject regarding AEs.
- As per Schedule of Events and Procedures ([Table 3](#)), perform the following procedures or assessments immediately before the 08:00 (±60 min) IOP measurement (all ophthalmic procedures to be performed in both eyes):
 - BCVA (before the 08:00 (±60 min) IOP measurement)
 - If more than 10 letters in BCVA were lost compared to the screening visit, then refraction should be performed again.
 - Slit-lamp biomicroscopy (before the 08:00 (±60 min) IOP measurement)
 - Perform vital signs (blood pressure/pulse rate) measurements (before the 08:00 (±60 min) IOP measurement).
 - Obtain urine and perform a urine pregnancy test, if the subject is a female of childbearing potential (before the 08:00 (±60 min) IOP measurement).
- Perform IOP measurement at 08:00 (±60 min).
- Instill study medication/eye drop after the 08:00 IOP measurement in both eyes. Authorized unmasked study staff should make sure the instillation is performed. Record the morning medication in subject diary.
- Perform IOP measurement at 10:00 (±60 min), and 16:00 (±60 min).
- Perform pupil dilation in both eyes after the 16:00 (±60 min) IOP measurement.
- Perform ophthalmoscopy with pupil dilation in both eyes immediately after the 16:00 IOP measurement.
- Perform GQL-15 questionnaire at any time during this visit.
- An authorized unmasked study staff member, other than the Investigator or Examiner, must:
 - Collect all used and unused bottles of study medication.
 - Collect the paper subject diary.

- If the subject provided written consent to provide a blood sample for a future PGx laboratory research study, the sample must be collected at this visit, if not collected at the previous visits.
- Exit the subject from the study.
- Inform the subjects they will be contacted to confirm AEs by phone call approximately 2 weeks post last study drug administration.

Note:

- **If the study drug administration is discontinued prior to Visit 5, then to the extent possible, all procedures for Study Exit/Early Termination as per Table 3 will be performed on the day of early termination. Subjects who are discontinued from the study early will not be replaced.**
- **If subject requires an unscheduled visit, procedures and assessments will be performed as needed.**

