4.4. Schedule of Events and Procedures

The schedule of events and procedures is provided in [Table 3](#).

Table 3: Schedule of Events and Procedures

	Washout Period		Double-Masked Treatment Period				Follow-up Period
	Visit 1 Screening *	Optional Visit 1a	Visit 2 Eligibility/Baseline *	Visit 3 Week 2	Visit 4 Week 6	Visit 5 Month 3 Exit or Early Termination ^a	2 weeks of post-Last Study Drug Administration
Study day	D-28		D1	D14	D42	D90	Study Exit + D14
Visit window in days	+7		NA	±3	±3	±7	+7
Signed and dated informed consent ^b	X						
Inclusion/Exclusion Criteria ^b	X		X				
Demographics and Medical History, including prior PGA ^c	X						
Other prior or Concomitant Medications/ and Therapies/Procedures	X	X	X	X	X	X	
Dosing Compliance Check				X	X	X	
AEs ^d	X	X	X	X	X	X	X
Pregnancy Test ^e	X		X		X	X	
Vital Signs (blood pressure/pulse rate) ^f	X		X (08:00)			X (08:00)	
Refraction ^g	X						
BCVA ^g	X	X	X (08:00)	X (08:00)	X (08:00)	X (08:00)	
Slit-lamp Biomicroscopy ^h	X	X	X (08:00)	X (08:00)	X (08:00)	X (08:00)	
IOP ⁱ	X	X	08:00	08:00	08:00	08:00	
			10:00	10:00	10:00	10:00	
			16:00	16:00	16:00	16:00	
Pachymetry ^j	X						
Instill study medication after IOP measurement at site by unmasked site staff and record dosing				X (08:00)	X (08:00)	X (08:00)	
Gonioscopy ^k	X						
Visual Field ^l	X						

Table 3: Schedule of Events and Procedures (Continued)

	Washout Period		Double-Masked Treatment Period				Follow-up Period 2 weeks of post-Last Study Drug Administration
	Visit 1 Screening	Optional Visit 1a	Visit 2 Eligibility/Baseline	Visit 3 Week 2	Visit 4 Week 6	Visit 5 Month 3 Exit or Early Termination ^a	
Study day	D-28		D1	D14	D42	D90	Study Exit + D14
Visit window in days	+7		NA	±3	±3	±7	+7
Ophthalmoscopy ^m	X		X (16:00)			X (16:00)	
Blood Sampling for PGx ⁿ						X	
Dispense Study Medication & Diary			X		X		
Collect Study Medication & Diary					X	X	
Phone call ^o				X	X	X	X
GQL-15 questionnaire ^p			X			X	

* Visit 1 (Screening) and Visit 2 (Eligibility/Baseline, Day 1) may be combined into one visit for treatment-naïve subjects as long as the additional requirements of Visit 2 (Eligibility/Baseline, Day 1) are fulfilled on the day of this combined visit; in particular, full diurnal IOP measurements (at 08:00, 10:00, 16:00) must be taken.

^a Optional at unscheduled visit, required for early terminated subjects.

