7.1. Subject Early Discontinuation/Withdrawal from the Study

An early termination occurs when a subject who provides written informed consent ceases participation in the study, regardless of circumstances, before the completion of the study. Subjects may be voluntarily discontinued from study medication or withdrawn from the study at any time for any reason. In addition, the Principal Investigator or Medical Monitor or designee may discontinue the study drug administration or terminate a subject's study participation due to any of the following reasons:

- AE (e.g., not compatible with study continuation)
- Non-compliance with study drug
- Lack of efficacy (e.g., IOP exceeds 34 mmHg in either eye after randomization)
- Progressive disease
- Protocol deviation (e.g., not fulfilling eligibility criteria)
- Pregnancy
- Voluntary withdrawal by subject at any time for any reason
- Lost to follow-up (e.g., no contact is possible)
- Death
- Other

If the study drug administration is discontinued prior to Visit 5, they should be encouraged to still participate in all follow-up study visits until Visit 5 on an observational basis.

If the study drug administration is discontinued prior to Visit 5, then to the extent possible, all procedures for Early Termination will be performed on the day of early drug discontinuation as per [Table 3](#). Subjects who are discontinued from the study early will not be replaced.

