8.6.4.2. Pregnancy Monitoring and Reporting Procedures

A urine pregnancy test will be conducted using a commercially available test kit at Visit 1 (Screening), Visit 2 (Baseline, Day 1), Visit 4 (Week 6) and Visit 5 Study Exit/Early Termination for all females of childbearing potential.

Although not considered an AE or SAE, pregnancy is an ESI and requires careful monitoring and follow up. If pregnancy is reported by a study subject (or in the partner of a study subject), the investigator must:

- Inform Santen within 24 hours of learning of the pregnancy.
- If the pregnancy has occurred in a study subject, discontinue further study medication administration and/or withdraw the subject from the study.
- Report pregnancy information on the eCRF following instructions.
- Follow the pregnancy until outcome is known. Santen will request specific follow-up on a case-by-case basis.

Additional details regarding collection, reporting, and follow-up of pregnancy is provided below:

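### The early-termination visit lists an on-site dose with no exemption for subjects whose drug has been stopped, and its exit step clashes with the off-drug follow-up in Section 7.1

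*Protocol*

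**What the plan says.** Protocol Table 3 (Section 4.4) has one column headed "Visit 5 Month 3 Exit or Early Termination". The row "Instill study medication after IOP measurement at site by unmasked site staff and record dosing" is marked at 08:00 for Visit 3, Visit 4 and that shared column. Footnote a to the column reads "Optional at unscheduled visit, required for early terminated subjects". SAP Table 1 repeats both the shared column and the mark.

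Section 8.1.6, whose heading names early termination, lists the step "Instill study medication/eye drop after the 08:00 IOP measurement in both eyes" and asks unmasked staff to see that it is done. Its closing note says that, when drug is stopped before Visit 5, "all procedures for Study Exit/Early Termination as per Table 3 will be performed on the day of early termination". Section 7.1 has the parallel sentence: "all procedures for Early Termination will be performed on the day of early drug discontinuation". Both sentences carry a qualifier limiting them to what is feasible.

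On stopping drug, Section 7.1 lists adverse events and pregnancy among the reasons for which administration may be discontinued. For a pregnant subject, Section 8.6.4.2 tells the investigator to "discontinue further study medication administration and/or withdraw the subject from the study". On follow-up after stopping, Section 7.1 says of such subjects that "they should be encouraged to still participate in all follow-up study visits until Visit 5 on an observational basis".

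**The concern.** On the day drug is stopped, one part of the protocol discontinues it and another schedules a further drop in each eye. A site that follows the checklist doses a subject taken off drug, perhaps because of an adverse event. A site that withholds the drop departs from a listed step. The protocol should not leave staff to choose between two written instructions on dosing.

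A second conflict affects data. A checklist that ends by exiting the subject on the day of drug discontinuation works against the off-drug attendance that 7.1 encourages. Post-discontinuation IOP can be lost as a result, although Protocol 9.7 and SAP 8.1.1.1 censor it only after other IOP-lowering treatment.

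**Working it through.** The core of this is a reading of text, so the passages are set side by side.

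1. **Is a dose at early termination really instructed?** Table 3 marks it in the shared column, footnote a applies the column to early-terminated subjects, and 8.1.6 repeats the step. Two other places presuppose it: Table 3 footnote f and Section 12.3.4 both put vital signs at early termination ahead of the morning dose. The entry is therefore more than a by-product of table layout.

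2. **Is anyone exempted?** No footnote to the instillation row, no bullet in 8.1.6 and no sentence in 7.1 removes the step for a subject whose drug has been stopped.

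3. **Adverse events.** Under 7.1 stopping is permitted rather than compulsory. Once the decision is taken, the procedures called for that day include another instillation. The conflict is direct, and nothing elsewhere resolves it.

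4. **Pregnancy.** Section 8.1.6 lists the urine test before the 08:00 IOP and the instillation after it, with no branch for a positive result. Sections 8.6.4.1 and 12.3.3 require the result before dosing, and 8.6.4.2 requires the drug to stop. Taken together these largely bar the dose; the checklist simply does not say so.

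5. **Follow-up visits.** Section 8.1.6 collects all bottles and exits the subject. Section 7.1 hopes to see the same subject through Visit 5. If she or he attends, the Visit 3, 4 and 5 checklists list instillation again, and the Visit 4 checklist also dispenses a new kit and reminds the subject to keep dosing. None has an off-drug branch.

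6. **Number affected.** The plan's figure is 280 evaluable subjects plus a 5% allowance: 280 x 0.05 = 14, and 280 + 14 = 294. The 14 cover drop-out for any cause, including loss to follow-up with no visit at all. The subset stopped for an adverse event or pregnancy who attend an early-termination visit is not given in either document.

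7. **Treatment end date.** SAP 4.1.3 defines exposure as end date minus start date plus 1. Assume the last home dose was the evening before the visit. A drop at the visit then moves the end date, and so the exposure, by 1 day. The treatment-emergent window (end date plus 2 days, SAP 4.3.1) moves by the same day. Separately, SAP 4.1.3 fills a missing last-dose date with the day before the early-termination visit, or the day before Month 3 for completers. That does not fit a schedule with a dose on the visit day.

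**The case against.** The best defence is that the specific provisions govern the general schedule. The feasibility qualifier gives sites room, attendance after stopping is described as observational, and the pregnancy rules come before any dose. Part of this stands. A reader might infer that the protocol orders a pregnant subject to be dosed; read together, Sections 8.6.4.1, 8.6.4.2 and 12.3.3 do not support that. The qualifier also means that the listed procedures are not absolute. But it speaks to feasibility and never mentions dosing, so it is not an exemption, and it leaves the adverse-event case open.

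Nor does every early termination conflict. If the visit is simply the last treatment day, a morning drop contradicts nothing, since completers receive one on their exit day. An IOP above 34 mmHg is only an example of a permitted reason to stop.

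A reader might also infer a biased efficacy comparison, because the 08:00 drop is active timolol in one arm and vehicle in the other. That difference is part of the design at every on-treatment visit, so the early-termination visit creates no new asymmetry. What remains unclear is whether the 10:00 and 16:00 readings at that visit count as on drug.

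The beta-blocker contraindications in exclusion 21 are screened out at entry. They do not show that a subject with such a condition would be dosed at early termination.

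**Conclusion.** The inconsistency is real. The schedule and visit checklist list a dose at early termination without exempting subjects whose drug has been stopped, which conflicts with the discontinuation provisions of 7.1. It is plainest for adverse events; for pregnancy the gap lies in the checklist rather than in the rules. The exit step also conflicts with the off-drug attendance in 7.1, and the later checklists do not provide for that attendance.

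The size cannot be stated as a count. It is tempting to take the 14 planned drop-outs as the number affected, but the documents give no rate for the relevant subset. The effect on treatment end date is about one day, assuming dosing continued to the evening before the visit. No effect on an efficacy conclusion is shown. The point rests on contradictory dosing instructions that bear on subject safety, and secondarily on retention of IOP data.

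**What to change.** - In Table 3, Section 8.1.6 and SAP Table 1, give the early-termination or drug-discontinuation visit its own column and checklist, or footnote it.
- Reconcile the instillation entry at that visit, and at later visits attended off drug, with 7.1 and 8.6.4.2 so that one instruction applies. Include footnote f, Section 12.3.4, and the kit dispensing and dosing reminder at Visit 4.
- Show in the checklist how a positive pregnancy test is handled, in line with the sections that already address it.
- Make the exit step agree with the 7.1 provision for attendance to Visit 5.
- Align the last-dose imputation in SAP 4.1.3 with whatever dosing instruction is adopted.

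Which clinical rule applies is for the sponsor to decide. The cost is a protocol amendment and matching SAP edits: one table column or a few footnotes and bullets. It needs no extra subjects, staff or scheduled visits.
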